9.3.3. Serious Adverse Event (SAE)

A SAE is any AE that in the view of either the Investigator or Sponsor, meets any of the following criteria:

- Results in death
- Is life threatening; that is, poses an immediate risk of death at the time of the event
An AE or suspected adverse reaction is considered "life-threatening" if, in the view of either the Investigator or Sponsor, its occurrence places the subject at immediate risk of death. It does not include an AE or suspected adverse reaction that, had it occurred in a more severe form, might have caused death
- Requires inpatient hospitalization or prolongation of existing hospitalization
Hospitalization is defined as an admission of greater than 24 hours to a medical facility and does not always qualify as an AE
- Results in a persistent or significant incapacity or substantial disruption of the ability to conduct normal life functions
- Results in a congenital anomaly or birth defect in the offspring of the subject (whether the subject is male or female)
- Important medical events that may not result in death, are not life-threatening, or do not require hospitalization may also be considered serious when, based upon appropriate medical judgment, they may jeopardize the subject and may require medical or surgical intervention to prevent one of the outcomes listed in this definition. Examples of such medical events include allergic bronchospasm requiring intensive treatment in an emergency room or at home, blood dyscrasias or convulsions that do not result in inpatient hospitalization, or the development of drug dependency or drug abuse

The terms "severe" and "serious" are not synonymous. Severity refers to the intensity of an AE (e.g., rated as mild, moderate, or severe, or according to National Cancer Institute Common Terminology Criteria for Adverse Events [NCI CTCAE]; OR Toxicity Grading Scale for Healthy Adult and Adolescent Volunteers Enrolled in Preventive Vaccine Clinical Trials; the event itself may be of relatively minor medical significance [such as severe headache without any further findings]).

Severity and seriousness need to be independently assessed for each AE recorded on the eCRF.

9.3.4. Adverse Event of Special Interest

For the purpose of this study, severe reductions in platelet count $< 50,000/\text{mm}^3$ accompanied by a major bleeding (MB) event or clinically-relevant non-major bleeding (CRNMB) event, or platelet count of $< 25,000/\text{mm}^3$ independent of a MB or CRNMB event are considered as AEs of special interest and should be subject to 15-day expedited reporting by the Sponsor to the regulatory agencies.

9.4. Monitoring and Recording Adverse Events

Any pre-existing conditions or signs and/or symptoms present in a subject prior to the start of the study (i.e., before informed consent) should be recorded as Medical History and not recorded as AEs unless the pre-existing condition worsened. The Investigator should always group signs and symptoms into a single term that constitutes a **single unifying diagnosis** if possible. Before a diagnosis is confirmed, all symptoms should be reported as separate AEs.

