3.7.2.1 Local Cutaneous Reactions at the Injection Site

Local cutaneous reaction at injection site (LCRIS) is defined as (A) moderate or severe Injection Site Erythema, Swelling, Pruritus, Pain or Tenderness that started on the day of injection, persisted for at least two days, i.e. event onset date on the day of injection and resolution date not on the day of injection or the day after the injection, will be included. Events with onset date on the day of injection and missing resolution date will also be included; or (B) any AE at the injection site, regardless of severity, that leads to discontinuation of study drug, where AE at the injection site is the principal reason for discontinuation.

Percentage of injections leading to local cutaneous reaction at the injection site will be calculated as follows for each subject: $(A/B)*100$, where A=number of injections with a LCRIS, and B=total number of injections. Doses that are split across multiple injections are counted as a single injection.

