3.7.2.2 Flu-like Reactions

Flu-like reactions will also be summarized by preferred term.

Flu-like reactions are defined as either (A) flu-like illness or (B) Pyrexia or feeling hot or body temperature increased, plus at least two of the following: Chills, Myalgia, and Arthralgia, starting on day of injection or the next day.

Percentage of injections leading to flu-like reactions will be summarized using the descriptive statistics.

Percentage of the injections leading to flu-like reactions will be calculated as follows for each subject: $(A/B)*100$, where A=number of injections leading to flu-like reactions, and B=total number of injections.

Flu-like reactions will be listed by preferred term.

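### The injection-site reaction (LCRIS) definition in SAP 3.7.2.1 names five signs but no grouped term, so a multi-sign reaction grouped under protocol 9.4 may be missed from the LCRIS percentage

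*Combined protocol and SAP*

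**What the plan says.** Protocol 9.4 sets the recording rule for adverse events. It begins "The Investigator should always group signs and symptoms into a single term that constitutes a" and goes on to require a single unifying diagnosis, qualified by 'if possible'. The next sentence gives the fallback: "Before a diagnosis is confirmed, all symptoms should be reported as separate AEs".

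SAP 3.7.2.1 defines an LCRIS in two limbs.

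- Limb (A) is "moderate or severe Injection Site Erythema, Swelling, Pruritus, Pain or Tenderness that started on the day of injection, persisted for at least two days". An event that starts on the injection day and has no resolution date is also included.
- Limb (B) is "any AE at the injection site, regardless of severity, that leads to discontinuation of study drug", provided that event is the main reason for stopping.

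The summary measure is a percentage for each subject, (A/B)*100, with "A=number of injections with a LCRIS, and B=total number of injections".

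SAP 3.7.2.2 is built differently: "Flu-like reactions are defined as either (A) flu-like illness or (B) Pyrexia or feeling hot or body temperature increased", where the second option also needs at least two further symptoms. It therefore accepts either the unifying term or the component symptoms.

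**The concern.** The recording rule and the counting rule are not joined up. The first steers sites towards one term for a cluster of signs where a diagnosis can be made. Limb (A) of the second recognises only the individual signs. The list in limb (A) is closed: it has no wording such as 'including', no composite entry, and no instruction for mapping a grouped record back to its signs.

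Take a moderate reaction with redness, swelling and pain after one injection. Recorded as three events, it counts. Recorded as one event called 'injection site reaction', it matches none of the five entries if the list is applied literally. Two sites could each follow 9.4 in good faith and yet contribute different LCRIS counts for the same reaction.

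At stake is one planned tolerability summary for a subcutaneously injected drug. Under the literal reading, grouping a reaction whose signs would each qualify can only take it out of the numerator.

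**Working it through.** The documents give no expected LCRIS rate and no figure to reproduce. The check is a comparison of texts, followed by simple arithmetic on the SAP's own formula.

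**Which records count if limb (A) is read literally** (moderate or severe, onset on the injection day, lasting at least two days)

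| How the reaction is recorded | Main reason for stopping Study Drug? | Counted as LCRIS? |
|---|---|---|
| One of the five signs alone | No | Yes, limb (A) |
| Several of the five signs, each as its own event | No | Yes, limb (A) |
| One grouped term | Yes | Yes, limb (B) |
| One grouped term | No | Matches neither limb |

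Only the last row is a gap. Separate recording does not inflate the measure, because the numerator counts injections with an LCRIS and not events: three signs after one injection count once.

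**Evidence within the SAP that a wider form was available.** Limb (B) of the same definition speaks of any adverse event at the injection site. The flu-like definition names a unifying term. Limb (A) does neither.

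**Inputs**

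- Injections per subject: 7 (protocol 3.4.3).
- Subjects: about 30, randomized 2:1 (protocol 3.3 and 3.4.3). This gives 30 × 2/3 = 20 active and 30 × 1/3 = 10 placebo.
- Assumption: all doses are given, so B = 7.
- Assumption: the per-subject percentages are averaged by arm. SAP 3.7.2.1 does not name the arm-level statistic; SAP 3.1 plans means among its general summaries.

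**Effect of one missed reaction**

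- On the subject: 1/B × 100 = 1/7 × 100 = 14.3 points. With fewer doses the step is larger, for example 1/5 × 100 = 20 points.
- On the active-arm mean: 14.3/20 = 0.71 points.
- On the placebo-arm mean: 14.3/10 = 1.43 points.

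**How many are missed.** This cannot be derived. It lies between zero (every sign recorded separately) and all multi-sign reactions that did not lead to discontinuation.

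For scale only, assume that 10% of the 20 × 7 = 140 active injections (14) truly led to a qualifying reaction and that a share g was recorded under a grouped term. The reported figure is then 10% × (1 − g): 10% at g = 0, 7.5% at g = 25%, 5.0% at g = 50% and 2.5% at g = 75%. Both the 10% and the values of g are assumptions, so this range is not an estimate.

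**The case against.** A reader might infer something stronger: that 9.4 always requires grouping, that an LCRIS can arise only from the five signs, and that multi-sign reactions recorded as instructed are therefore not counted. The documents do not support that.

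- The grouping rule concerns a diagnosis and applies only if possible. Neither document calls an injection-site reaction a diagnosis. A site that lists redness, swelling and pain separately because no diagnosis is confirmed also complies with 9.4, and limb (A) counts those events. It does not follow that compliant sites report fewer reactions than non-compliant ones.
- Limb (B) counts an injection-site event under any term and at any severity if it is the main reason for stopping.
- The SAP does not say that limb (A) is a strict search on preferred terms. It could be read as describing which signs qualify, with a grouped record reviewed for its content.
- Protocol 9.4.3.2 and Appendix D refer to grading of injection-site events. The part of Appendix D available to this review covers hematology and chemistry only. Any injection-site rows there, or guidance in the eCRF instructions, could bear on how these events are recorded.
- The flu-like comparison is imperfect. That definition describes a syndrome needing several symptoms, whereas limb (A) needs only one local sign.
- LCRIS is not a listed endpoint. The safety endpoint in protocol 1.2.3 and SAP 1.3.3 is TEAE incidence and severity. Grouped reactions still enter the SAP 3.7.2 tables by preferred term, relationship and severity.
- A reader might also infer that the loss falls on the more extensive reactions and makes tolerability look better. Nothing in the documents shows that more signs means a more extensive reaction, or that any loss will occur.

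These points turn a certain undercount into a possible one and confine it to a single summary. They do not close the gap: neither document says how a grouped injection-site term is to be handled, and the natural reading of a closed list leaves it out.

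**Conclusion.** The point holds as a risk of undercounting. A moderate or severe multi-sign reaction recorded under one grouped term, and not the main reason for stopping Study Drug, may be missed from the LCRIS percentage.

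This rests on two conditions: that some sites treat such a reaction as a unifying diagnosis, and that limb (A) is applied literally. If either fails, nothing is lost. If both hold, each missed reaction costs the amount shown above, and the total cannot be known in advance.

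The general TEAE tables, the efficacy analyses and the platelet events of special interest are unaffected. The case for a change is that the SAP leaves the handling unstated, that for a reaction with qualifying signs the error can only go downwards, and that the remedy is small.

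**What to change.** Preferred change, in SAP 3.7.2.1 limb (A): also count a moderate or severe grouped injection-site term, such as 'Injection Site Reaction', when the event as recorded includes at least one of the five named signs or does not specify its signs. The same onset and duration rules apply. Tying the term to the five signs keeps out grouped events that are known to contain none of them. This change also covers records that sites have already grouped.

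Alternative, in protocol 9.4 or the eCRF instructions: ask sites to record each injection-site sign as its own adverse event, as an exception to the grouping rule. This leaves the SAP definition untouched but does not help records already grouped, and it raises the number of separate events in the general TEAE counts. One of the two changes is enough.

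The cost is one phrase in the SAP or one sentence of recording guidance, with no effect on dosing or patient management. The LCRIS percentage may be slightly higher. A grouped event is graded as a whole, so it may qualify as moderate where no single sign would, and an event with unspecified signs may include none of the five.

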9.4.1. Serious Adverse Events

In the interest of subject safety, and in order to fulfill regulatory requirements, all SAEs (regardless of their relationship to Study Drug) should be reported to the Sponsor or designee within 24 hours of the Study Center's first knowledge of the event. The collection of SAEs will begin after the subject signs the informed consent form and stop at the end of the subject's follow-up period which is defined as Study Day 127. When the Investigator is reporting by telephone, it is important to speak to someone in person vs. leaving a message. SAEs should be reported using an electronic SAE submission form whenever possible. In situations where the electronic SAE submission is unavailable, an Initial Serious Adverse Event Form should be completed and a copy should be faxed to the Sponsor or designee. The SAE reporting instruction, including the fax number and email address, for reporting SAEs can be found in the Study Reference Manual for the study.

Detailed information should be actively sought and included on Follow-Up Serious Adverse Event Forms as soon as additional information becomes available. All SAEs will be followed until resolution. SAEs that remain ongoing past the subject's last protocol-specified follow-up visit will be evaluated by the Investigator and Sponsor. If the Investigator and Sponsor agree the subject's condition is unlikely to resolve, the Investigator and Sponsor will determine the follow-up requirement.

9.4.2. Non-Serious Adverse Events

The recording of non-serious AEs will begin after the subject signs the informed consent form and will stop at the end of the subject's follow-up period, which is defined as Study Day 127 / Week 19. The Investigator will monitor each subject closely and record all observed or volunteered AEs on the Adverse Event Case Report Form.

9.4.3. Evaluation of Adverse Events (Serious and Non-Serious)

The Investigator's opinion of the following should be documented on the Adverse Event Case Report Form:

9.4.3.1. Relationship to the Study Drug

The event's relationship to the Study Drug is characterized by 1 of the following:

- **Related:** There is clear evidence that the event is related to the use of Study Drug, e.g., confirmation by positive re-challenge test

- **Possible:** The event cannot be explained by the subject's medical condition, concomitant therapy, or other causes, and there is a plausible temporal relationship between the event and Study Drug administration
- **Unlikely/Remote:** An event for which an alternative explanation is more likely (e.g., concomitant medications or ongoing medical conditions) or the temporal relationship to Study Drug administration and/or exposure suggests that a causal relationship is unlikely (For reporting purposes, Unlikely/Remote will be grouped together with Not Related)
- **Not Related:** The event can be readily explained by the subject's underlying medical condition, concomitant therapy, or other causes, and therefore, the Investigator believes no relationship exists between the event and Study Drug

9.4.3.2. Severity

The severity of AEs and SAEs relating to laboratory test and adverse events at the injection site may be graded based on criteria from the Common Terminology Criteria for Adverse Events (CTCAE) Version 5.0, November 2017 (refer to [Appendix D](#)) and the Investigator should classify events and laboratory findings as mild, moderate, or severe based on the clinical significance of the event and laboratory finding in the study subject. Any AE not listed in [Appendix D](#) will be graded as follows:

- **Mild:** The event is easily tolerated by the subject and does not affect the subject's usual daily activities
- **Moderate:** The event causes the subject more discomfort and interrupts the subject's usual daily activities
- **Severe:** The event is incapacitating and causes considerable interference with the subject's usual daily activities

If the event is an SAE, then all applicable seriousness criteria must be indicated (criteria listed in Section [9.3.3](#))

9.4.3.3. Action Taken with Study Drug

Action taken with Study Drug due to the event is characterized by one of the following.

- **None:** No changes were made to Study Drug administration and dose
- **Not Applicable:** SAE/AE was reported during Screening Period prior to Study Drug administration
- **Permanently Discontinued:** Study Drug was discontinued and not restarted
- **Temporarily Interrupted, Restarted – Same Dose:** Dosing and/or dosing frequency was temporarily interrupted/changed or delayed due to the AE and restarted at the same dose
- **Reduced Dose:** Dosing was reduced, temporarily interrupted or delayed due to the AE and restarted at the next lower dose or reduced dosing frequency

9.4.3.4. Treatment Given for Adverse Event

Any treatment (e.g., medications or procedures) given for the AE should be recorded on the Adverse Event Case Report Form. Treatment should also be recorded on the concomitant treatment or ancillary procedures eCRF, as appropriate.

9.4.3.5. Outcome of the Adverse Event

If the event is a non-serious AE, then the event's outcome is characterized by 1 of the following:

- **AE Persists:** Patient terminates from the trial and the AE continues
- **Recovered:** Patient recovered completely from the AE
- **Became Serious:** The event became serious (the date that the event became serious should be recorded as the Resolution Date of that AE and the Onset Date of the corresponding SAE)
- **Change in Severity (if applicable):** AE severity changed

If the event is an SAE, then the event's outcome is characterized by 1 of the following:

- **Ongoing:** SAE continuing
- **Persists (as non-serious AE):** Patient has not fully recovered but the event no longer meets serious criteria and should be captured as an AE on the non-serious AE eCRF (the SAE resolution date should be entered as the date of onset of that AE)
- **Recovered:** Patient recovered completely from the SAE (the date of recovery should be entered as the SAE resolution date)
- **Recovered with Sequelae:** The signs/symptoms of the reported SAE have improved but not completely resolved, and a new baseline for the subject is established since full recovery is not expected
- **Fatal:** Patient died (the date of death should be entered as the SAE resolution date)
- **Unknown:** The outcome of the reported SAE is not available, e.g., patient is lost to follow-up

9.4.3.6. Follow-up of Adverse Event

Investigator Follow-Up

During the study period, the Investigator should follow each AE until the event has resolved to baseline grade or better, the event is assessed as stable, the patient is lost to follow-up, or the patient withdraws consent. Every effort should be made to follow all SAEs considered to be related to Study Drug or related to study procedures until a final outcome can be reported.

Resolution of AE (with dates) should be documented on the Adverse Event eCRF and in the patient's medical record to facilitate source data verification.

Investigator should follow-up or support the Sponsor's effort to follow-up with all pregnancies reported during the study from either the study subject or the female partner of male study subject until pregnancy outcome is available.

Sponsor Follow-Up

For SAEs, AESI and pregnancy cases in subjects who have completed or terminated study, the Sponsor or a designee should follow-up by telephone, fax, email, and/or a monitoring visit to obtain additional case details and outcome information (e.g., from hospital discharge summaries, consultant reports, autopsy reports) in order to perform an independent medical assessment of the reported case.

9.5. Procedures for Handling Special Situations

9.5.1. Abnormalities of Laboratory Tests

Clinically-significant abnormal laboratory test results may, in the opinion of the Investigator, constitute or be associated with an AE. Examples of these include abnormal laboratory results that are associated with symptoms, or require treatment, e.g., bleeding due to thrombocytopenia, tetany due to hypocalcemia, or cardiac arrhythmias due to hyperkalemia. Whenever possible, the underlying diagnosis should be listed in preference to abnormal laboratory values as AEs. Clinically-significant abnormalities will be monitored by the Investigator until the parameter returns to its baseline value or until agreement is reached between the Investigator and Sponsor Medical Monitor. Laboratory abnormalities deemed not clinically-significant (NCS) by the Investigator should not be reported as AEs. Similarly, laboratory abnormalities reported as AEs by the Investigator should not be deemed NCS on the laboratory sheet.

The Investigator is responsible for reviewing and signing all laboratory reports. The signed clinical laboratory reports will serve as source documents and should include the Investigator's assessment of clinical significance of out of range/abnormal laboratory values.

9.5.2. Prescheduled or Elective Procedures or Routinely Scheduled Treatments

A prescheduled or elective procedure or a routinely scheduled treatment will not be considered an SAE, even if the subject is hospitalized; the Study Center must document all of the following:

- The prescheduled or elective procedure or routinely scheduled treatment was scheduled (or was on a waiting list to be scheduled) prior to obtaining the subject's consent to participate in the study
- The condition that required the prescheduled or elective procedure or routinely scheduled treatment was present before and did not worsen or progress in the opinion of the Investigator between the subject's consent to participate in the study and the timing of the procedure or treatment
- The prescheduled or elective procedure or routinely scheduled treatment is the sole reason for the intervention or hospital admission

9.5.3. Dosing Errors

Study Drug errors (including overdose, underdose, and administration error) should be documented as Protocol Deviations. A brief description should be provided in the deviation, including whether the subject was symptomatic (list symptoms) or asymptomatic, and the event accidental or intentional.

Dosing details should be captured on the Dosing Case Report Form. If the subject takes a dose of Study Drug that exceeds protocol specifications and the subject is symptomatic, then the symptom(s) should be documented as an AE and be reported per Section 9.4.

An overdose is the accidental or intentional use of a drug in an amount higher than the dose being studied. An overdose or incorrect administration of study treatment is not itself an AE, but it may result in an AE. All AEs associated with an overdose or incorrect administration of Study Drug should be recorded on the Adverse Event eCRF. If the associated AE fulfills seriousness criteria, the event should be reported to the Sponsor immediately (i.e., no more than 24 hours after learning of the event).

Should an overdose occur, the Investigator or designee should refer to the Guidance to Investigator's section of the Investigator's Brochure and contact the Sponsor or designee within 24 hours.

